9.4.1.1 Worsening of hearing

A worsening of hearing in the treated ear is not to be recorded as AE. Any change of hearing thresholds and word recognition scores is subject of analysis under this protocol. The subject's subjective sensations will be captured by patient reported outcome measures (HHIA, PGIC).

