10.2 Safety endpoints

10.2.1 Primary safety endpoint

Occurrence of clinically relevant hearing deterioration (defined as increase in air conduction hearing threshold ≥ 10 dB at the average of any two contiguous test frequencies) from baseline to FUV3 in the treated ear. The analysis will also be conducted with bone conduction hearing threshold values.

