10.2.2 Secondary safety endpoints

- Occurrence of clinically relevant hearing deterioration in the treated ear (air conduction) from baseline to all FUVs (other than FUV3);
- Difference in occurrence of clinically relevant hearing deterioration from baseline to all FUVs between treated and untreated contralateral ear;
- Occurrence and severity of Adverse Events (AEs) and Serious Adverse Events (SAEs), assessed for causal relationship with respect to:
 - o The IMP;
 - o The intratympanic IMP administration procedure.

11 Statistical methods and data analysis

A statistical analysis plan (SAP) will detail the statistical evaluation. This plan is finalized prior to unblinding. In particular, changes of planned analyses outlined in the trial protocol will be documented in the SAP. Deviations from the approved SAP will be documented in the clinical trial report.

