5.1.2.1 Main Secondary Efficacy Endpoint

[figure not shown]
• Absolute improvement in WRS (80dB) from baseline to FUV4. An improvement in WRS of at least 15 percentage points is considered clinically relevant.

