5.2 SAFETY ENDPOINTS

5.2.1 Primary Safety Endpoints

Occurrence of clinically relevant hearing deterioration (defined as increase in air conduction hearing threshold \geq 10 dB at the average of any two contiguous test frequencies) from baseline to FUV3 in the treated ear. The analysis will also be conducted with bone conduction hearing threshold values.

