Table 14.2.2.1	Summary of WRS(80 dB) and Change from Baseline to Follow-up Visits: (Efficacy Analysis Set)
Table 14.2.2.2	Summary of WRS(80 dB) and Change from Baseline to Follow-up Visits: (Per-Protocol Analysis Set)
Section 14.2.3	Other Secondary Efficacy Parameter
Table 14.2.3.1	Summary of Complete Hearing Recovery Frequency from Baseline to FUV3 and FUV4: (Efficacy Analysis Set)
Table 14.2.3.2.1	Summary of Complete Tinnitus Remission Frequency by Visit: (Efficacy Analysis Set)
Table 14.2.3.2.2	Summary of Tinnitus Loudness and Tinnitus Annoyance and Change from Baseline by Visits: (Efficacy Analysis Set)
Table 14.2.3.3	Summary of WRS _(60 dB) and Change from Baseline to Follow-up Visit 4: (Efficacy Analysis Set)
Table 14.2.3.4	Summary of Hearing Handicap Inventory for Adults Scores by Visits: (Efficacy Analysis Set)
Table 14.2.3.5.1	Categorical Summary of Patient Global Impression of Change (PGIC) in Hearing Loss Severity by Visits: (Efficacy Analysis Set)
Table 14.2.3.5.2	Numeric Summary of Patient Global Impression of Change (PGIC) in Hearing Loss Severity by Visits: (Efficacy Analysis Set)
Table 14.2.3.6.1	Summary of No Improvement in PTA (< 15 dB) Frequency from Baseline to FUV3 and FUV4: (Efficacy Analysis Set);
Table 14.2.3.6.2	Summary of No Marked Improvement in PTA (< 30 dB) Frequency from Baseline to FUV3 and FUV4: (Efficacy Analysis Set).
Section 14.3	Safety Data Summary Tables
Section 14.3.1	Adverse Events
Table 14.3.1.1	Overall Summary of Treatment-Emergent Adverse Events (TEAE): (Safety Analysis Set)
Table 14.3.1.2	Subjects with Treatment-Emergent Adverse Events by System Organ Class and Preferred Term: (Safety Analysis Set)
Table 14.3.1.3	Subjects with Treatment-Emergent Adverse Events by Preferred Term: (Safety Analysis Set)
Table 14.3.1.4	Subjects with Serious Treatment Emergent Adverse Events by System Organ Class and Preferred Term: (Safety Analysis Set)
Table 14.3.1.5	Subjects with Treatment-Emergent Adverse Events Resulting in Study Withdrawal by System Organ Class and Preferred Term: (Safety Analysis Set)
Table 14.3.1.6	Subjects with Treatment-Emergent Adverse Events by System Organ Class, Preferred Term and Severity: (Safety Analysis Set)
Table 14.3.1.7	Subjects with Treatment-Emergent Adverse Events by System Organ Class, Preferred Term and Study Drug Relationship: (Safety Analysis Set)

Number	Title

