Table 14.3.1.8	Subjects with Treatment-Related Treatment-Emergent Adverse Events by System Organ Class and Preferred Term: (Safety Analysis Set)
Table 14.3.1.9	Subjects with Administration Procedure Related Treatment- Emergent Adverse Events by System Organ Class and Preferred Term: (Safety Analysis Set)
Table 14.3.1.10	Subjects with Treatment-Related Serious Treatment-Emergent Adverse Events by System Organ Class and Preferred Term: (Safety Analysis Set)
Table 14.3.1.11	Subjects with Administration Procedure Related Serious Treatment- Emergent Adverse Events by System Organ Class and Preferred Term: (Safety Analysis Set)
Table 14.3.1.12	Subject with Treatment-Emergent Adverse Events Leading to Death by SOC and PT: (Safety Analysis Set)
Section 14.3.2	Listings of Deaths, Other Serious and Significant Adverse Events
Table 14.3.2.1	On Study AEs Resulting in Deaths, Listing
Table 14.3.2.2	Serious Treatment-Emergent Adverse Events, Listing
Table 14.3.2.3	Treatment-Emergent Adverse Events Leading to Permanent Discontinuation of Study Drug, Listing
Section 14.3.4	Abnormal Laboratory Value (each patient)
Section 14.3.4.1	Clinical Laboratory Data
Section 14.3.4.1.1	Hematology Data
Table 14.3.4.1.1.1	Summary of Hematology Value and Change from Baseline: (Safety Analysis Set)
Table 14.3.4.1.1.2	Hematology Shift from Baseline: (Safety Analysis Set)
Section 14.3.4.1.2	Biochemistry Data
Table 14.3.4.1.2.1	Summary of Biochemistry Value and Change from Baseline: (Safety Analysis Set)
Table 14.3.4.1.2.2	Biochemistry Shift from Baseline: (Safety Analysis Set)
Section 14.3.4.1.3	Virology Data Summary of Virology Value: (Safety Analysis Set)
Table 14.3.4.1.3 Section 14.3.4.2	Vital Signs
Table 14.3.4.2.1	Summary of Vital Signs and Change from Baseline: (Safety Analysis Set)
Section 14.3.4.3	Other Safety Summaries
Table 14.3.4.3.1	Summary of Pure Tone Audiometry in Air Conduction and Change from Baseline in All Frequencies: (Safety Analysis Set)
Table 14.3.4.3.2	Summary of Hearing Deterioration by Air Conduction: (Safety Analysis Set)
Table 14.3.4.3.3	Summary of Pure Tone Audiometry in Bone Conduction and Change from Baseline in All Frequencies: (Safety Analysis Set)
Table 14.3.4.3.4	Summary of Hearing Deterioration by Bone Conduction: (Safety Analysis Set)

Number	Title
Table 14.3.4.3.5	Analysis in occurrence of Clinically Relevant Hearing Deterioration Between Treated and Untreated Ear: (Safety Analysis Set)

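### Treated-ear loss of word recognition is kept out of AE recording, but hearing deterioration is defined and counted in the Safety Analysis Set for pure tone thresholds only

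*Protocol*

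**What the plan says.** Protocol 9.4.1 sets the general rule that a condition present at baseline which worsens is reported as an AE. Section 9.4.1.1 makes an exception: "A worsening of hearing in the treated ear is not to be recorded as AE". The reason given is that "Any change of hearing thresholds and word recognition scores is subject of analysis under this protocol", and it adds that HHIA and PGIC will capture what the subject perceives.

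The primary safety endpoint (Protocol 10.2.1, SAP 5.2.1) is clinically relevant hearing deterioration, "defined as increase in air conduction hearing threshold ≥ 10 dB at the average of any two contiguous test frequencies", repeated with bone conduction. The secondary safety endpoints (Protocol 10.2.2, SAP 5.2.2) extend it to the other follow-up visits and compare treated with untreated ear. SAP Section 16 provides matching tables, among them "Summary of Hearing Deterioration by Air Conduction: (Safety Analysis Set").

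Word recognition appears as efficacy. Improvement in WRS at 80 dB to FUV4 is the main secondary endpoint, for which "An improvement in WRS of at least 15 percentage points is considered clinically relevant" (SAP 5.1.2.1; Protocol 10.1.2 says the same). The planned table is "Summary of WRS(80 dB) and Change from Baseline to Follow-up Visits: (Efficacy Analysis Set"), with a Per Protocol version; WRS at 60 dB has one table in the Efficacy Analysis Set. Speech audiometry is described under Protocol 6.6, Safety Assessments, and is done at 80 dB at every follow-up visit except the conditional one.

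**The concern.** The exemption removes an event type from the AE tables and offers an analysis in exchange. For thresholds the exchange is complete: there is a harm criterion, a safety population and a count by arm. For word recognition the only analysis is of efficacy, with a relevance limit stated for gains and none for losses.

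A treated subject whose speech recognition falls while thresholds stay within the 10 dB criterion is therefore neither an AE nor a safety event. Recovery of speech discrimination is a separate secondary objective, so the plan does not treat thresholds as a full substitute for it. Harm to hearing is also not hypothetical in this programme: Protocol 2.3.2 reports treatment-related impaired hearing in 6 patients (4.0%) and one related SAE of neurosensory deafness on AM-111. At stake is whether the study report can state how many subjects per arm lost speech recognition.

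**Working it through.** **1. Coverage check.** The plan states no figure to reproduce here, so the first step is to compare the two hearing functions.

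| | Pure tone thresholds | Word recognition |
|---|---|---|
| Treated-ear worsening recorded as AE | No (Protocol 9.4.1.1) | No (same section) |
| Criterion for relevant loss | At least 10 dB, two contiguous frequencies | None; 15 points stated for improvement only |
| Safety endpoint | Protocol 10.2, SAP 5.2 | None |
| Safety Analysis Set count by arm | Tables 14.3.4.3.2, 14.3.4.3.4, 14.3.4.3.5 | None |
| Other display | Tables 14.2.1.1, 14.2.1.2; listings | Tables 14.2.2.1, 14.2.2.2, 14.2.3.3; Listings 16.2.6.9, 16.2.6.10 |

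The endpoint lists and the Section 16 table list are readable in full, so redaction does not explain the empty cells. The Efficacy Analysis Set also requires a valid PTA at baseline and after treatment (SAP 6.2). Treated subjects without these drop out of the WRS tables as well.

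**2. What the planned WRS summary shows.** SAP 7.1 and 9 give n, mean, SD, minimum, Q25, median, Q75 and maximum. Suppose k of n subjects in an arm lose L points and the rest gain g:

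mean = [(n - k) x g - k x L] / n

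The values of k, L and g are assumptions. The arm size is 56/3 = 18.7, about 19, or 100 as planned.

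- n = 19, k = 4, L = 20, g = 30: mean = (15 x 30 - 4 x 20)/19 = 370/19 = +19.5; SD 20.9; Q25 = median = Q75 = +30; minimum -20. The share with a loss is 4/19 = 21%.
- Same values with k = 5: mean = (14 x 30 - 5 x 20)/19 = 320/19 = +16.8; Q25 falls to +5 or -20, depending on the quantile rule. With k = 6, Q25 is -20.
- n = 100, L = 15, g = 18.3 (the Day 7 difference from placebo at 80 dB in Protocol 2.3.1, borrowed only as an illustrative gain): k = 10 gives (90 x 18.3 - 150)/100 = +15.0; k = 20 gives (80 x 18.3 - 300)/100 = +11.6. Q25 reaches -15 at k = 26.

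The minimum reveals one loser. The lower quartile moves only when about a quarter of the arm has lost. In between, the number of losers cannot be read from the table.

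**3. Chance rate of a 15-point drop.** Protocol 6.6.5.4 uses lists of 40 to 50 words. For an unchanged ear with true score p, take two independent scores X and Y, each Binomial(m, p), and compute P[(X - Y)/m >= 0.15]. This needs a drop of 8 words of 50 (16 points) or 6 of 40 (15 points).

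| p | 50 words | 40 words |
|---|---|---|
| 0.3 | 5.1% | 8.9% |
| 0.5 | 6.7% | 10.9% |
| 0.8 | 3.0% | 6.1% |
| 0.9 | 0.6% | 2.0% |

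The range is about 1-11%. If all 19 subjects in an arm could show a loss, that is 19 x 0.006 = 0.1 to 19 x 0.109 = 2.1 subjects per visit by chance.

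**4. Choice of reference for low baselines.** A subject starting below 15% cannot fall by 15 points. Measuring such a subject's loss from the best earlier follow-up visit looks attractive. But for FUV4 against the best of FUV1 to FUV3, simulation of an unchanged ear at p = 0.3 to 0.5 gives 12-15% chance losses with 50 words and 20-24% with 40. It would also mix two reference points in one percentage.

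**The case against.** The strongest reply is that 9.4.1.1 says only that WRS changes are analysed, and they are: by arm, at every scheduled follow-up visit, in two analysis sets. It promises neither a safety endpoint nor a count. That stands. A reader might infer that the statement is untrue for word recognition, but the documents do not support that.

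A reader might also infer that speech loss is buried inside a mean improvement. That too goes further than the documents. Minimum, quartiles and SD are planned, and Listings 16.2.6.9 and 16.2.6.10 show every randomized subject's scores, so a reviewer could count losses by hand. They would, however, have to choose a loss limit after seeing the data, because none is prespecified.

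PGIC deserves some credit. It measures change, so it needs no baseline; it is given at FUV2, FUV3 and FUV4, and Table 14.2.3.5.1 counts its categories. But it rates hearing loss severity in general, is tabulated in the Efficacy Analysis Set, and cannot isolate speech. HHIA has no baseline and starts at FUV3.

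The uncounted case is also narrow. Speech loss with a qualifying threshold rise at any two contiguous frequencies is already caught, and low baseline scores limit measurable loss. The documents give neither the frequency of speech loss without a threshold rise nor the share with low baselines. Finally, the two-value illustration is favourable to the concern: 4 of 19 is the largest number of losers that leaves Q25 untouched.

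**Conclusion.** The point holds in a limited form. Following the plan as written gives no count by arm of treated subjects who lose word recognition without a threshold rise of at least 10 dB at two contiguous frequencies. Such losses are visible in the efficacy-set distribution summaries and the listings, but are not counted as harm.

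How many subjects this concerns is unknown. The illustration shows only that about a fifth of an arm could lose speech recognition without moving any quartile; its gains and losses are assumed. Reading 15 points as the limit for a relevant loss is also an assumption, since the documents state that limit for improvement. The chance rates assume independent binomial scores and an unchanged true score.

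This is a gap in safety reporting, not an error in a planned result. With 56 subjects and descriptive analysis only (SAP 2.2), the case for closing it is that the data are already collected and the cost is small.

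**What to change.** Add to SAP 10.1.2 and Section 16 one descriptive Safety Analysis Set table: number and percentage of subjects, per arm and follow-up visit, whose treated-ear WRS at 80 dB has fallen by at least 15 percentage points from baseline. Label the limit as an assumption that mirrors the improvement limit. Use as denominator the subjects with baseline WRS of at least 15% and a score at that visit. Report separately the number per arm with baseline below 15%, who cannot show such a loss, and do not measure their loss from a best earlier visit. Cite the table in Protocol 9.4.1.1, so that the AE exemption points to the analysis that replaces it.

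The cost is one extra table, with no new data collection. The downside is noise: with a chance rate of roughly 1-11% per test, up to about two subjects per arm at a visit may appear as losses without any true change. A footnote should say that rates are to be read against placebo and are descriptive only.

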9.4.1.2 Worsening of tinnitus

A worsening of tinnitus in the treated ear is not to be recorded as AE. Any change in tinnitus loudness or tinnitus annoyance is the subject of analysis under this protocol.

The occurrence of new tinnitus in the treated or untreated ear should be recorded as AE.

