2.3.2 Summary of accumulated adverse event data

A total of 221 subjects were included in the two clinical trials conducted with AM-111 (AM-111-AAT-PI, AM-111-CL-08-01). Seventy-five subjects received a single dose AM-111 at a concentration of 0.4 mg/mL (low dose), 74 subjects received AM-111 at the concentration of 2.0 mg/mL (high dose) and 72 subjects were randomized to receive the matching placebo.

In subjects who received any dose of AM-111, 57 patients reported at least 1 adverse event, of which 18 reported treatment-related AEs. Only four treatment-related adverse event terms were reported in more than 1 patient, and these were tinnitus (7 patients, 4.7%), hearing impaired (6 patients, 4.0%), ear pain (3 patients, 2.0%), and incision site complications (2 patients, 1.3%). Ear discomfort, vertigo, autophony, otitis externa, otitis media, nausea and otoacoustic emission test abnormal were each reported by 1 patient. One serious adverse event (SAE) of deafness neurosensory was considered related to study drug. No fatal or life-threatening AE was reported.

The majority of AEs were local, mild or moderate in severity and concerned hearing and tinnitus. Detailed analysis of hearing deterioration at Days 3 and 7 pointed most often to the ongoing underlying pathology as cause; three cases were related to the myringotomy, and one case to middle ear infection (fully resolved). The majority of tinnitus-related AEs was observed only after Day 7 and thus considered unrelated. The number of subjects with procedure-related AEs (ear discomfort or pain, incision site complications, middle ear infection) was < 5%. By Day 7, the tympanic membrane was closed again in all patients except 7 (mild, fully resolved subsequently). Vital signs essentially remained stable throughout the observation period, and the incidence of spontaneous nystagmus decreased in all treatment groups. Further details of the adverse event profile are provided in the Investigator Brochure of AM-111.

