In the two clinical trials conducted with AM-111 to date, there were no apparent differences in frequency, intensity or relationship of local AEs between treatment groups. AEs were of transient nature, and there were no indications of dose-limiting adverse reactions of the IMP. While previous trial protocols did not differentiate between drug-emergent and procedure-emergent AEs, treatment-related local AEs can be presumed to be procedure-related in their entirety since no difference was observed between treatment groups. This is further supported by the observation that most of the local AEs occurred during or around the time of IMP administration.

Local events (mostly ear and labyrinth disorders) were transient and accounted for approximately 60% of reported treatment emergent adverse events (TEAEs), most frequently "hearing impaired" and "tinnitus". The frequency of occurrence of clinically relevant hearing deterioration (defined as \geq 15 dB averaged at 2 contiguous frequencies in the previous studies) overall was low (1-7% for all trial visits), and there was no statistically significant difference between treatment groups. In all treatment groups,

few subjects experienced a worsening of their tinnitus and even fewer the onset of new tinnitus in the treated ear in the first 7 days following the treatment (< 6%). These cases were likely related to the procedure or the underlying pathology and most were resolved by Day 30.

Accumulated clinical data do not show any effect of D-JNKI-1 on the vestibular function, as measured by the occurrence of spontaneous nystagmus.

Risks related to the background therapy (corticosteroids)

The risk of suppression of the hypothalamic-pituitary axis with a short course of corticosteroid treatment as proposed in this study is minimal. Nevertheless, corticosteroids should not be administered to patients with

- Hypersensitivity to any ingredients in the formulation;
- Systemic infections unless specific anti-infective therapy is employed;
- Ocular herpes simplex due to the possibility of perforation;
- Medical conditions which can be affected by corticosteroids, such as insulin-dependent or uncontrolled diabetes mellitus, tuberculosis, peptic ulcer, etc.

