9.4 Reporting

9.4.1 Trial specific rules for reporting

All AEs, including SAEs and clinically relevant abnormalities in laboratory test variables, will be monitored and documented from the time point of ICF sign off during TV until FUV4 (see Section 9.1).

The Investigator should ask the trial subject in a non-leading manner about the state of his/her health in order to elicit information on AEs which may have occurred since the last visit. Any clinically significant observations made during the visit itself also constitute AEs. The Investigator should make an assessment for AEs at each visit and record the events in the source documentation and in the CRF on the "Adverse Events" pages. Follow up information must be entered as soon as available.

Wherever possible, a specific disease or syndrome rather than individual associated signs and symptoms should be identified by the Investigator and recorded on the CRF. However, if an observed or reported sign, symptom or clinically significant laboratory abnormality is not considered a component of a specific disease or syndrome by the Investigator, it should be recorded as a separate AE in the source documents and on the CRF. Additionally, the condition that led to a medical or surgical procedure (e.g., surgery, endoscopy, tooth extraction, transfusion) should be recorded as an AE, not the procedure.

Any medical condition already present at the baseline medical assessment will be documented as medical history. If a medical condition or signs or symptoms present at baseline worsens (e.g. change in severity or seriousness) at any time during the trial, this should be reported as an AE.

SAEs will be followed until the event resolves or stabilizes or up to 2 months after FUV4. The Investigator is obliged to assist with the follow-up of SAEs. In case a SAE occurs after the subject has completed the trial and the Investigator considers this event related to the IMP or trial procedures, it should be reported immediately. The Investigator must contact the CRO Safety Manager to determine how the SAE should be documented and reported.

Any AE that is still ongoing after a subject's final visit will be recorded as ongoing in the CRF. However the Investigator will continue to follow up ongoing SAEs for the time frame described above and record information in the source documents and on the *Follow-Up SAE Form*.

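### Worsening of existing treated-ear tinnitus is exempt from AE recording, and no planned safety table counts the subjects who worsen

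*Protocol*

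**What the plan says.** **AE rule.** Protocol 9.4.1.2 states "A worsening of tinnitus in the treated ear is not to be recorded as AE". The ground given is that "Any change in tinnitus loudness or tinnitus annoyance is the subject of analysis under this protocol". The exemption has a limit: "The occurrence of new tinnitus in the treated or untreated ear should be recorded as AE". The general rule in Protocol 9.4.1 points the other way. "If a medical condition or signs or symptoms present at baseline worsens (e.g. change in severity or seriousness) at any time during the trial", it should be reported as an AE.

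**Described risk.** Protocol 2.5.2, under risks related to the IMP, reports that in the earlier trials "few subjects experienced a worsening of their tinnitus and even fewer the onset of new tinnitus in the treated ear" during the first 7 days, at a rate below 6%. Protocol 2.3.2 gives tinnitus as the most frequent treatment-related AE term, with 7 patients (4.7%). Safety and local tolerance is a stated secondary objective.

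**Planned safety analysis.** Protocol 10.2 and SAP 5.2 name hearing deterioration and AEs/SAEs as the safety endpoints. None of the Safety Analysis Set tables listed in SAP Section 16 names tinnitus.

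**Where the ratings do appear.**
- SAP Table 14.2.3.2.2 is titled "Summary of Tinnitus Loudness and Tinnitus Annoyance and Change from Baseline by Visits: (Efficacy Analysis Set". SAP Section 9 gives the statistics: n, mean, SD, minimum, quartiles, median and maximum.
- Table 14.2.3.2.1 counts remission only.
- Listing 16.2.6.3 (visit ratings) and Listing 16.2.6.4 (weekly diary) cover each randomized subject.

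**The concern.** The exemption rests on a promise that the change will be analysed. For hearing, which Protocol 9.4.1.1 exempts in the same way, the promise is kept by a defined threshold, an endpoint and by-arm safety tables. For tinnitus, the visible plan offers efficacy summaries of rating change and listings, and no count of subjects who got worse.

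This matters because the two directions of change are not symmetric. The subject instruction in the protocol's tinnitus appendix says that tinnitus often disappears after acute hearing loss. Remitters therefore pull the average change toward improvement, and a minority who worsen can sit behind a favourable mean and median. AE tables would show no worsening of existing treated-ear tinnitus, because it is not recorded there. A reader of the safety section would have no figure by arm for a risk that the protocol itself describes.

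The SAP's changes from the protocol also drop the loudness and annoyance ratings from the definition of complete remission. After that change, none of the endpoints in SAP Section 5 uses them.

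**Working it through.** **1. The plan's own figure.** Exposed to AM-111 in the earlier trials: 75 + 74 = 149 (Protocol 2.3.2). Treatment-related tinnitus: 7/149 = 4.7%, as stated. The next most frequent term, hearing impaired, is 6/149 = 4.0%, also as stated.

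**2. The two exempted events side by side.**
- *AE recording:* both are exempt in the treated ear (Protocol 9.4.1.1 and 9.4.1.2).
- *Threshold for worsening:* hearing, a rise of at least 10 dB averaged over any two contiguous frequencies; tinnitus, none.
- *Safety endpoint:* hearing, primary and secondary; tinnitus, none.
- *Safety Analysis Set tables:* hearing, Tables 14.3.4.3.2, 14.3.4.3.4 and 14.3.4.3.5; tinnitus, none listed.
- *Count by arm:* hearing, yes; tinnitus worsening, no output title names it.

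**3. What Table 14.2.3.2.2 would show.** The rating scales are not visible, so this example rests on assumptions: a 0-10 scale, remitters changing by -6, worseners by +3, everyone else by 0, and 19 subjects per arm (56/3 = 18.7). With r remitters and w worseners, mean change = (-6r + 3w)/19.

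With r = 8 (about 40%):
- w = 0: -48/19 = -2.53
- w = 1 (5%): -45/19 = -2.37
- w = 2 (11%): -42/19 = -2.21
- w = 4 (21%): -36/19 = -1.89

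Over r = 4 to 10 (about 20-50%) and w = 0 to 6 (up to about 30%), the mean runs from -60/19 = -3.16 to (-24 + 18)/19 = -0.32, so it is always negative. The median never rises above 0. The upper quartile stays at 0 up to w = 4 and first moves, to 1.5, at w = 5 (26%). The maximum reads +3 as soon as w = 1, and reads the same at w = 6. The table can show that someone worsened, but not how many did.

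**4. How many cases might be involved.** The documents give no rate for worsening alone, so the rate is an assumption with a range: 2%; 4.7% (the earlier related-AE rate, borrowed); and 6% (the ceiling in Protocol 2.5.2). With 56 subjects allocated 1:1:1, about 56 x 2/3 = 37 are on active drug.
- Expected cases: 37 x 0.02 = 0.74; 37 x 0.047 = 1.74; 37 x 0.06 = 2.22.
- Chance of at least one, 1 - (1 - rate)^37: 0.53, 0.83 and 0.90.

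Under 9.4.1.2, none of these cases would appear in an AE table if it is a worsening of existing treated-ear tinnitus.

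**The case against.** The case on the other side is substantial, and most of it limits how far the point can go.

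- *A reader might infer that worsening survives only as a mean.* It does not. The planned table also gives quartiles and the maximum, and Listing 16.2.6.3 shows every randomized subject's ratings by visit. With 56 subjects, someone could count the worseners by hand. That stands, but it leaves a safety count for the reader to assemble.
- *A reader might infer that tinnitus AEs in general are suppressed.* They are not. New tinnitus in either ear is an AE and reaches the Safety Analysis Set AE tables. As worded, the exemption covers only worsening in the treated ear.
- *A reader might take 4.7% as the rate of lost events.* The figure mixes new and worsened tinnitus, so it cannot size the loss. Protocol 2.3.2 adds that most tinnitus-related AEs arose after Day 7 and were considered unrelated. Protocol 2.5.2 reports no apparent difference in local AEs between groups.
- *The specific rule may simply override the general one.* That is the natural reading, and 9.4.1 refers to 9.4.1.2 for documentation details. But the general sentence carries no exception.
- *Using the Efficacy Analysis Set probably loses few subjects.* Visit ratings and audiometry fall at the same follow-up visits. That stands. The main defect is the missing count, and the choice of set is secondary.
- *Some text is not visible,* including SAP material between 9.2.2 and Section 10 and part of Protocol 11.6.2. The point therefore rests on the readable endpoint lists and on the titles in SAP Section 16.

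**Conclusion.** The point holds as a gap in the planned safety outputs. Worsening of existing treated-ear tinnitus is exempt from AE recording, has no safety endpoint, and is counted by arm in no listed table, while the parallel exemption for hearing has all the counterparts. The earlier 7/149 shows that the risk is relevant; it does not give the expected number of missed cases. At assumed rates of 2% to 6%, that number is about 0.7 to 2.2 among some 37 actively treated subjects, taking the 56 enrolled as randomized and treated.

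A reader might go further and conclude that the local-tolerance objective is left unanswered, or that the report would hide harm. The documents do not support that. New-tinnitus AEs, procedure-related AEs, otoscopy and tympanometry all bear on tolerance, and the individual ratings are listed. No primary result changes and the analysis is descriptive throughout, so this is an inexpensive improvement to safety reporting. It does not threaten the trial's conclusions.

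**What to change.** **Add one descriptive table on the Safety Analysis Set,** named in SAP 10.1.2 as the counterpart of the 9.4.1.2 exemption. By arm, at each of FUV1 to FUV4 and for any post-baseline visit, give the number and percentage of subjects with tinnitus at baseline whose TLQ(Loudest) or TAQ(Worst) rises above its baseline value. Use any increase as the definition. Add a larger cut-off only if it can be justified from the rating scale, since the visible documents give no basis for one.

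**Reconcile Protocol 9.4.1 with 9.4.1.2,** so that the general rule on worsening of baseline symptoms and the tinnitus exemption do not conflict. The CSR should say which rule governed the recorded AEs.

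**Cost.** One SAP paragraph and one table, from ratings already scheduled from TV to FUV4; no new data. The drawback is that any-increase counts include ordinary rating noise, more so for the any-visit row. The placebo column shows how much.
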